9.2.3 Pooling of Site Data

The primary analysis will be based on the pooled results. However, the homogeneity of study outcomes across investigational sites will be examined.

The primary justification for pooling is that investigational sites will be following the same protocol, using the same device system, and following the same Instructions for Use/AMPLEX Surgical Manual. Additionally, frequent contact and monitoring of the sites will be performed to ensure that all investigational sites are evaluating participants and recording study results in a reliable and reproducible manner. It is not anticipated that any individual investigational site will dominate the study results. Therefore, it is considered that these procedures will ensure that the data from these investigational sites can be combined and analyzed.

To evaluate differences among sites and regions (US or non-US) in the trial, summaries for important baseline variables, such as demographics, foot and ankle related medical history and baseline clinical variables, and variables related to procedures will be presented by site and by region as described in Section 7.

Poolability across investigational sites will be tested for the primary endpoint using the homogeneity test of risk difference proposed by Zhang, Yang, & Cho (2009) (5) at a two-sided 5% significance level. If all the subjects in a site are randomized to one treatment group, the site will be excluded from this assessment. The same test will also be used to assess the homogeneity of risk difference among regions. If there is statistically significant heterogeneity across investigational sites, the implications for the interpretation of the primary analysis will be discussed.

9.3 Secondary Endpoint(s)

9.3.1 Key Secondary Endpoint

The key secondary efficacy endpoint will be the proportion of subjects who meet the following criteria for the CT radiographic fusion success at 52 weeks:

- Radiographic evidence of fusion by CT scan ($\geq 50\%$ bone bridging across the joint space for the full complement of joints in the absence of secondary surgical or nonsurgical interventions intended to promote fusion)

Non-inferiority of AMPLEX to ABG will be claimed if the lower bound of the 2-sided 90% CI for the difference of the proportions (AMPLEX minus ABG) is greater than -12.0%. The superiority will be claimed if the lower limit of the 2-sided 95% CI is greater than zero. The CI will be constructed with the normal approximation to the binomial.

A subject will be considered a CT radiographic fusion success if he/she has $\geq 50\%$ bone bridging across the joint space by the CT scan for all treated joints without secondary surgical or nonsurgical interventions intended to promote fusion, otherwise, the subject will be considered a CT radiographic fusion failure. The CT radiographic fusion response status will be determined for 12, 24, and 52 weeks. The response status will be assessed for each time point based on the windowed analysis visits. The response status for the absence of secondary interventions to promote fusion will be assessed in a period up to the actual visit date that the corresponding CT images for a particular analysis visit were collected. If any of the components of the CT radiographic fusion success criteria at an analysis visit is missing, the response status will be considered missing for the analysis visit.

For the key secondary analysis, the last available CT radiographic fusion response status will be used (i.e., the last observation carried forward; LOCF) if the response status at 52 weeks is missing. If no CT radiographic response status data are available at previous visits, the response status at 52 weeks will be considered failure.

The same set of sensitivity analyses as for the primary endpoint will be conducted for the key secondary endpoint. These sensitivity analyses will be conducted regardless of the testing results of the primary efficacy endpoint. Therefore, no multiplicity among sensitivity analyses will be adjusted.

9.3.2 Other Secondary Endpoints

The following other secondary efficacy endpoints will be assessed without multiplicity adjustments.

- Proportion of subjects achieving CT radiographic fusion success at 12 and 24 weeks (in the absence of secondary surgical or nonsurgical interventions intended to promote fusion)
- Change from baseline in pain on weight-bearing at fusion site at 12, 24, and 52 weeks (>20 mm reduction from baseline on 100 mm VAS)

- ABG harvest site pain at 2, 6, 12, 24 and 52 weeks (<20 mm on 100 mm VAS)
- Change from baseline in FAAM-ADL at 12, 24 and 52 weeks
- SPC at 12 and 24 weeks
- Change from baseline in Short Form-12 (SF-12) at 24 and 52 weeks

The difference of the proportions of subjects achieving CT radiographic fusion success between treatment groups will be estimated with the 2-sided 90% and 95% confidence intervals at 12 and 24 weeks. Similarly, the difference of the proportions of subjects meeting all the criteria for SPC between treatment groups will also be estimated at 12 and 24 weeks. In addition, the response status for each component of SPC will also be summarized. The missing values will be left as missing.

The change from baseline in FAAM-ADL and weight-bearing pain at fusion site at 12, 24 and 52 weeks will be analyzed by repeated-measures analysis of covariance (ANCOVA) models that includes treatment, time, treatment-by-time interaction, baseline value, presence of non-union risk factors (none vs. any of obesity, diabetes, and previous ankle/hindfoot surgery, or smoking history) at baseline, and fusion sites (single, double, or triple hindfoot, or ankle). The adjusted changes from baseline and their difference between treatment groups will be estimated for each time point. The overall difference over 52 weeks will be estimated as the main effect for treatment in the model. In addition, the proportion of subjects achieving ≥ 8 points improvement from baseline in FAAM-ADL and the proportion of subjects achieving ≥ 20 mm reduction from baseline in weight-bearing pain at fusion site will be summarized by treatment group at each visit. The missing values will be left as missing.

The ABG harvest site pain at 2, 6, 12, 24 and 52 weeks will be summarized for the ABG group. The proportion of subjects with < 20 mm in ABG harvest site pain will also be summarized at each visit.

The change from baseline in SF-12 scores (PCS and MCS) at 24 and 52 weeks will be analyzed by the repeated measures ANCOVA using the similar ANCOVA models described for FAAM-ADL. Each score will be calculated based on the algorithm to be provided by the licensee.

The FAAM-ADL score will be calculated based on the algorithm described in [Appendix 2](#).

10 Safety

10.1 General Considerations

Safety parameters will be evaluated for the safety analysis set, and the data will be reported according to actual graft material received.

10.2 Adverse Events

Adverse events (AEs) will be classified according to the MedDRA version effective at trial start or later. The version of the MedDRA used for the final analyses will be documented.

A pre-treatment AE will be defined as an AE occurring before the initiation of the surgery. All AEs occurring after the initiation of the surgery will be considered treatment-emergent AEs (TEAEs).

If the timing of an AE cannot be established in relation to the initiation of the surgery, it will be considered as a treatment emergent AE.

Pre-treatment AEs will be reported in a listing only. This listing will be sorted by investigational site, subject ID and date of onset.

Any potential device, procedural, or ancillary device related AEs and all events associated with secondary surgical intervention will be adjudicated for the severity and relatedness by the Clinical Events Committee (CEC). The type of the secondary surgical intervention will also be adjudicated. In the adverse event summaries, the adjudicated data will be used for those events.

The relationship to device (i.e., graft material), ancillary device, index surgical fusion procedure, or bone graft harvest procedure will be evaluated as definitely, probably, possibly, unlikely, unrelated, or unknown. Any events evaluated as definitely, probably, possibly, or unknown will be classified as related.

Device related AEs will include all AEs classified as related to the graft material. Procedure related AEs will include all AEs classified as related to the index surgical fusion procedure or the bone graft harvest procedure.

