ABG provides an effective osteoconductive scaffold for new bone formation and contains appropriate growth factors and cells to potentiate new bone formation (osteoinductive). The availability of locally-harvested bone in ankle or foot arthrodesis can be limited, therefore, a second harvest site is often required from either the iliac crest, proximal or distal tibia to facilitate the acquisition of enough bone to support the graft substitute application. Harvesting ABG, however, is associated with both short- and long-term morbidity. Complications of autograft harvest include blood loss, postoperative pain, fracture, infection, other non-infectious wound complications, heterotopic bone formation, hernia, and nerve injury. Baumhauer and colleagues recently

reported the results of a prospective randomized study of patients undergoing ankle and hindfoot fusion procedures using ABG harvested from one of four sites (iliac crest, proximal tibia, distal tibia, and calcaneus). Clinically significant pain at the bone graft harvest site was reported by 35% of patients 3 weeks postoperatively and 18% had persistent pain up to 1 year. A review of the literature suggests that the overall complication rate from tibial graft sites, although it has become a favored source for autograft material for foot and ankle surgery, is 5.5%. These complications range in severity from hematoma/seroma and paresthesia to infection, fracture and invasion of the joint space.

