#### **7.2.2.4 Graft Harvest Site Pain**

Since AMPLEX subjects will not undergo graft harvest, this is a patient reported outcome that is applicable to ABG subjects only. Subjects in the ABG group will be asked to assess the pain associated with their graft site. ABG subjects will assess the pain using a VAS. Subjects will mark the location on a 100-millimeter line corresponding to the amount of pain they experienced with 0 mm being “no pain” and 100 mm being “the worst pain imaginable”. This questionnaire will be completed at 2, 6, 12, 24 and 52 weeks after surgery. The assessment and its instructions for use will be provided in the SRM.

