### 8.2.2 Recording of Adverse Events

All adverse events will be coded by system organ class and preferred term using the Medical Dictionary for Regulatory Activities (MedDRA) (version effective at trial start).

During each clinical follow-up, the Investigator or Investigator designee will determine AE occurrences. Each adverse event is considered to be either anticipated or unanticipated as described above. The site is required to report all adverse events that occur during the trial. AEs will be collected from the time of informed consent until the final follow up.

Post-treatment outcomes that are evaluated as efficacy endpoints, such as pain on weight-bearing, harvest site pain, etc., will not be reported as AEs. Post-operative pain is, in general, anticipated, typically improves over time, and it will not be considered an AE. However, surgical site pain that is associated with a complication, or worsens over time, may be considered an AE.

Any abnormal laboratory test results or other safety assessments (e.g., vital signs measurements, etc.) considered to be clinically significant in the medical and scientific judgment of the Investigator are to be recorded as AEs.

The sign and symptoms and/or clinical sequelae resulting from lack of efficacy will be reported if they fulfill the definition of an AE or SAE.

Internal fixation medical devices (e.g., screws, plates, pins and staples) are being used in this study and are considered ancillary devices. Medical device events associated with these ancillary devices, including those resulting from screw loosening or malfunctions of the ancillary device, must be documented and reported as adverse events by the Investigator throughout the study.

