**Table 5 AE Severity Grading Scale**

Severity Grade	Description
Mild (1)	Transient or mild discomfort; no limitation in activity; no medical intervention or therapy required. The subject may be aware of the sign or symptom but tolerates it reasonably well.
Moderate (2)	Moderate limitation in activity, minimal medical intervention/therapy required.
Severe (3)	Marked limitation in activity, medical intervention/therapy required hospitalizations possible.

**Device Related Adverse Event:** Relationship to the graft material will be assigned *one* of the following:

- **Definitely:** Clear evidence event caused by graft material; strong temporal relationship and an alternative cause is unlikely.

- **Probably:** Reasonable probability event might be caused by graft material. The event has a temporal relationship to the study procedure(s), and follows a known pattern of response and an alternative cause seems unlikely.
- **Possibly:** Reasonable possibility event is caused by graft material. The event has a temporal relationship to the study procedure(s) and follows a known pattern of response, but a potential alternative cause may be present.
- **Unlikely:** Evidence that there may be other causes and the relationship to the graft material, although cannot be completely ruled out, is remote.
- **Unrelated:** Cause of the event is known and the event is in no way related to any aspect of the graft material.
- **Unknown:** Causality cannot be determined.

The causality of AEs will be determined by the Investigator, and the CEC will adjudicate it.

In addition to the graft material, the relationship to the following will also be determined for each AE, if possible:

- **Ancillary Device Adverse Event:** An adverse event which is determined to be a consequence of an ancillary device and is not specifically related to the use of graft material, but could be related to the placement of the graft material. An ancillary device is defined as an approved medical device used in conjunction with the graft material, and used during the study procedure (e.g., internal fixation screws, etc.)
- **Procedure-Related Adverse Event:** An adverse event which is determined to be a consequence of the arthrodesis or harvest procedure and is not specifically related to use of the graft material or ancillary devices, but could be related to the placement of the graft material or ancillary devices.

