1.1 Definitions/ Abbreviations

1.1.1 Definition of Terms

Terms	Definitions
Screened	Signed the informed consent form
Screen failed	Discontinued from the trial prior to randomization
Device	AMPLEX or ABG
Procedure	Index surgical fusion procedure or bone graft harvest procedure

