10.2.1 Overview of Treatment-Emergent Adverse Events

An AE overview summary table will be prepared including the number of subjects reporting an AE, the percentage of subjects with an AE, and the number of events reported, for the following categories:

- Unanticipated adverse device effect
- Any TEAEs
- Device related AEs
- Procedure related AEs

- Deaths
- Serious adverse events (SAEs)
- Device related SAEs
- Procedure related SAEs
- AEs leading to secondary surgical interventions

The relationship to device or procedure will be

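### The single procedure-related class adds harvest events that only ABG subjects can have, so it does not compare fusion-procedure events like with like; ancillary-device relatedness has no output of its own

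*SAP*

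**What the plan says.** SAP 10.2 specifies four separate relatedness ratings: "The relationship to device (i.e., graft material), ancillary device, index surgical fusion procedure, or bone graft harvest procedure will be evaluated as" one of six levels. Definite, probable, possible and unknown all count as related. The SAP then merges two of the four: "Procedure related AEs will include all AEs classified as related to the index surgical fusion procedure or the bone graft harvest procedure". Its definition of terms does the same, with procedure meaning "Index surgical fusion procedure or bone graft harvest procedure". The protocol also uses one combined definition (8.2.3, text under Table 5): "An adverse event which is determined to be a consequence of the arthrodesis or harvest procedure".

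The overview table (SAP 10.2.1) and the SOC/PT tables (SAP 10.2.2) carry device-related AEs and SAEs, procedure-related AEs and "Procedure related SAEs". Protocol 9.7.2 has the same categories. Neither document plans a row, table or listing that separates fusion-procedure from harvest-procedure events.

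On who has a harvest, Protocol 7.2.2.4 says of harvest site pain: "Since AMPLEX subjects will not undergo graft harvest, this is a patient reported outcome that is applicable to ABG subjects only".

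On ancillary devices, Protocol 8.2.2 requires sites to report as adverse events "Medical device events associated with these ancillary devices, including those resulting from screw loosening or malfunctions of the ancillary device". The CEC adjudicates them (Protocol 3.3.1, SAP 10.2). No output in SAP 10.2.1 or 10.2.2 is defined by ancillary-device relatedness.

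**The concern.** The index fusion is the operation both arms share, so it is where a safety comparison of the two graft materials is like with like. The pooled row adds to the ABG side a second operation that AMPLEX subjects never have. If AMPLEX subjects had more events attributed to the fusion procedure, harvest events in the ABG column could shrink, cancel or reverse the visible difference. A reader of the procedure-related row could then conclude that the fusion procedure went equally well in both arms when the table does not show that.

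The ancillary-device gap is related. Screws, plates, pins and staples hold the fusion under test, and the SAP has the relation of each event to them rated. Without an output on that rating, a difference between arms in hardware-attributed events must be pieced together from general tables.

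**Working it through.** The plan gives no figure on this point, so there is none to reproduce. The check has two parts.

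**1. Size of the offset**

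Inputs:
- Planned arms: 320 AMPLEX, 160 ABG (Protocol 3.2).
- h, the proportion of ABG subjects with a harvest-related AE. The only non-pain figure is in Protocol 1.1, where "the overall complication rate from tibial graft sites" is given as 5.5%. It is a literature rate for tibial sites only, and other harvest sites are allowed, so I assume a range of 3% to 10%.
- The 18% one-year harvest pain figure in Protocol 1.1 is not used, because harvest site pain is not reported as an AE (Protocol 8.2.2, Appendix 1).
- f, the proportion of ABG subjects with a fusion-procedure AE. It is not in the documents; I assume 5%, 10% and 20%.
- Harvest and fusion events are assumed independent within a subject.

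Formulas:
- Pooled ABG rate = 1 − (1 − f)(1 − h) = f + h(1 − f).
- The pooled AMPLEX rate is its fusion-procedure rate alone.
- AMPLEX excess that pooling cancels exactly = h(1 − f).

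| h | f = 5% | f = 10% | f = 20% |
|---|---|---|---|
| 3% | 0.03 × 0.95 = 2.85 points | 2.70 | 2.40 |
| 5.5% | 0.055 × 0.95 = 5.2 points | 4.95 | 4.40 |
| 10% | 0.10 × 0.95 = 9.5 points | 9.0 | 8.0 |

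Hypothetical example, f = 10%, AMPLEX 15%, h = 5.5%:
- Fusion-procedure row alone: 48/320 (15.0%) against 16/160 (10.0%). Difference +5.0 points; SE = √(0.15 × 0.85/320 + 0.10 × 0.90/160) = 0.0310; 95% CI −1.1 to +11.1.
- Pooled row as planned: ABG rate = 1 − 0.90 × 0.945 = 14.95%. Difference 15.0 − 14.95 = +0.05 points; SE = √(0.15 × 0.85/320 + 0.1495 × 0.8505/160) = 0.0345; 95% CI −6.7 to +6.8.
- If no subject had both kinds of event, the ABG rate would be 10 + 5.5 = 15.5% and the difference −0.5 points.

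At h = 10%, a true +5-point excess would show as 5.0 − 9.5 = −4.5 points (f = 5%) to 5.0 − 8.0 = −3.0 points (f = 20%).

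As a measure of visibility only, take a true 20% against 10% at 320 and 160 (two-sided 5%, pooled variance under the null). A separate fusion row would have 82% power. The pooled row would have 51%, 26% and 4% at h = 3%, 5.5% and 10%.

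**2. Whether another planned output supplies the comparison**

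- *Device-related rows.* They capture events attributed to the graft. But the protocol's procedure-related definition (8.2.3), while excluding events specifically tied to graft or hardware, still admits events that may be linked to how these were placed. Some events relevant to the graft comparison can therefore sit in the pooled row.
- *SOC/PT rows.* They separate the sites only partly. Protocol Appendix 1 anticipates wound infection, cellulitis, wound breakdown, nerve damage, muscular damage and hemorrhage for surgery in general and also for harvest. Fracture is listed for both fusion surgery and harvest.
- *Listing of procedure-related AEs (SAP 10.2.2).* It gives subject-level detail, not rates by arm.
- *Ancillary-device events.* They fall within all TEAEs, TEAEs by severity, SAEs and AEs leading to secondary surgery (SAP 10.2.2). Hardware condition is summarised from imaging (SAP 10.4.3). None of these uses the relatedness rating.

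**The case against.** The strongest reply is that the pooled row is correct for its purpose. Avoiding harvest morbidity is the stated benefit of AMPLEX (Protocol 1.3 and 1.4), and the pooled class matches the safety component of the primary composite. This stands. A reader might infer that the row is biased or wrong; the documents do not support that. It answers a different question from the fusion-only comparison.

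Second, a reader might infer that a fusion-site excess with AMPLEX would be hidden from the safety report. That is too strong. Graft-attributed events have their own AE and SAE rows, where possible and unknown relations count as related. The CEC adjudicates blinded to treatment (Protocol 3.3.1). Secondary surgical interventions are by definition at the index fusion site (Protocol 8.1) and are summarised by type (SAP 10.3). Non-union, graft integrity and graft migration are summarised per treated joint (SAP 10.4.3). The offset therefore concerns only events attributed to the procedure and not to the graft.

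Third, a reader might infer that ancillary-device events go unreported. They do not: they appear in the general outputs named above, and the core laboratory reads screw loosening on X-ray (Protocol 7.2.1.1). What is missing is an output based on relatedness.

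Fourth, the 15% against 10% example is hypothetical. That is right: the fusion-procedure rates are assumed, and the 5.5% covers tibial sites only. The direction of the effect does not depend on them.

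Finally, SAP 10.2.1 ends with a sentence on relatedness that is incomplete in the text available. It may have been lost in extraction, and nothing here rests on it.

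**Conclusion.** The point holds in limited form. The planned procedure-related class measures total procedural burden and does not compare fusion-procedure events like with like, because only ABG subjects have a harvest. An AMPLEX excess in events attributed to the fusion procedure could be offset by h(1 − f): 2.4 to 2.9 points at a 3% harvest event rate, 4.4 to 5.2 at 5.5%, and 8.0 to 9.5 at 10%. These figures assume ABG fusion-procedure rates of 5% to 20% and independence; they are illustrations, not forecasts. Separately, ancillary-device relatedness is rated and adjudicated but has no AE row, table or listing of its own. Neither gap touches the primary test. Both affect how the safety comparison of a pivotal trial can be read.

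**What to change.** In SAP 10.2.1 and 10.2.2, add rows and SOC/PT tables, for AEs and for SAEs, for:
- events related to the index fusion procedure, in both arms, as the comparative row;
- events related to the harvest procedure, for subjects who received ABG only;
- events related to an ancillary device, in both arms, with a matching listing.

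Keep the pooled procedure-related row, labelled as the total.

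The cost is SAP text and table shells. SAP 10.2 already specifies the four ratings, so no new data should be needed. Because Protocol 8.2.3 defines one combined procedure relation and the eCRF is not among the documents, confirm that the fusion and harvest relations are recorded and adjudicated as separate fields. No hypothesis test, error rate or sample size changes.
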